## Protocol Summary

Title	Multi-Center Pilot Study of truSculpt Device
Objective	An exploratory pilot study to evaluate the safety, efficacy and ergonomics of Cutera truSculpt device
Study Design	Multi-center, exploratory pilot study
Enrollment	Approximately 40 subjects at three sites within the US
Safety Endpoint	Incidence and severity of adverse device events.
Exploratory Endpoints	[REDACTED] [REDACTED]. GAIS at 12 weeks post first and final treatment from Baseline. [REDACTED] [REDACTED] [REDACTED] [REDACTED] [REDACTED]
Subject Population	Female and male subjects between the ages of 18-65
Planned Schedule	First subject enrolled: August 2017 Last subject last visit: May 2018

## 1 PURPOSE

The purpose of this pilot study is to evaluate the truSculpt device.

## 2 BACKGROUND INFORMATION

[figure not shown]
[figure not shown]
Unwanted excess fat pockets/bulges have been among the top concerns expressed by patients in the aesthetic field. Although surgical interventions produce the most definitive results with body contouring, these invasive methods require significant recovery time and come with inherent risks.

As a non-invasive option, laser, intense pulsed light (IPL), RF, or a combination of these technologies have been developed to reduce cellulite and body circumference with minimal recovery time and risks [1]. The tightening effect of the thermal energy generated by these devices has been used for reduction in cellulite and body circumference in areas including but not limited to arms, abdomen, thigh, back and flanks [2-14]. Although lasers and IPLs can target the deep dermal layers, the thermal effects of these devices are limited due to light scattering and energy absorption by water in the dermis.

[figure not shown]
RF, which is the most studied device in the non-ablative category, uses electrical current rather than light energy. Unlike light energy, radio waves can penetrate deeper depending on the frequency of operation. RF can be used with all Fitzpatrick skin types without jeopardizing epidermal integrity [15].

Magnitude of thermal energy generated is dependent on the resistance (impedance) of the target tissue. When RF energy is conducted electrically to tissue, heat is produced as the tissue's inherent resistance (impedance) converts the electrical current to thermal energy [(J) = I x R x T where I = current, R = tissue impedance, and T = time of application)]. Subcutaneous fat which is a high impedance tissue generates greater heat and accounts for the deeper thermal effects of RF devices [15-18].

RF may be delivered in three different ways: 1) Monopolar when energy is applied as current between a single electrode tip and a grounding plate. 2) Bipolar when energy is applied between two points on the tip of a probe. 3) Unipolar when energy is delivered as the emission of electromagnetic radiation (EMR) rather than current and no grounding pad is necessary. This could be achieved by capacitive, inductive or resonant electrical coupling with the tissue.

temporary reduction in circumference of the abdomen [510(k) number K162512]. The treatment settings

### 3 STUDY OBJECTIVES

The objectives of this exploratory pilot study are to evaluate the safety, efficacy and ergonomics of the Cutera truSculpt RF device.

### 4 STUDY DESIGN

This is a multi-center, pilot study in approximately 40 subjects, ages 18 to 65. Subjects may receive [REDACTED] treatments and will be followed at 12 weeks post [REDACTED] final treatment.

#### 4.1 Study Endpoints

##### 4.1.1 Safety Endpoint

- Incidence and severity of adverse device events.

##### 4.1.2 Exploratory Endpoints

- [REDACTED]

- GAIS at 12 weeks post first and final treatment from Baseline.

- [REDACTED]

- [REDACTED]

#### 4.2 Study Duration

Subjects enrolled in this trial will be asked to participate for approximately 10 months, depending on treatment(s).

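### Do 10 months of participation per subject contradict a study calendar that runs only from August 2017 to May 2018?

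*Protocol*

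**What the plan says.** The Protocol Summary sets the calendar under Planned Schedule: "First subject enrolled: August 2017" and "Last subject last visit: May 2018". It plans for "Approximately 40 subjects at three sites within the US".

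Section 4.2 (Study Duration) gives the only readable figure for one subject's time in the study: "Subjects enrolled in this trial will be asked to participate for approximately 10 months, depending on treatment(s").

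Section 4 words the number of treatments permissively ("Subjects may receive", followed by a redacted number) and places follow-up 12 weeks after the "final treatment". Section 4.1.2 lists the readable efficacy endpoint as "GAIS at 12 weeks post first and final treatment from Baseline".

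The readable text states no enrolment period. Section 6 (Study Procedures) is blacked out, and Appendix 1 (Study Schedule) appears in the table of contents but cannot be read.

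**The concern.** Taken at face value, one subject's participation is as long as the entire study. About 40 subjects at three sites cannot all enrol on the first day, so a calendar with no enrolment period looks impossible.

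The possible consequences would be real. If the May 2018 date were enforced, subjects who enrolled late could lose their last treatments or the assessment 12 weeks after the final one. GAIS would then be missing in a way tied to enrolment date. Section 9.2 restricts the analysis set to enrolled subjects who complete treatment, so a course cut short would also remove the subject from analysis. Section 7.3 follows adverse events until resolution or until participation ends, so early closure would shorten safety follow-up too.

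**Working it through.** **Inputs.** First enrolment is in August 2017 and the last visit in May 2018, with no day given (Protocol Summary). Participation is about 10 months, depending on treatment (Section 4.2). The last assessment is 12 weeks, or 84 days, after final treatment (Sections 4 and 4.1.2). One month is taken as 30.4375 days.

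**Step 1: length of the calendar.** The protocol states no span in months, so there is no figure to reproduce. Span = last-visit date minus first-enrolment date.

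- Longest, 1 August to 31 May: 303 days; 303 / 30.4375 = 9.95 months.
- Mid-month to mid-month: 273 days; 273 / 30.4375 = 8.97 months.
- Shortest, 31 August to 1 May: 243 days; 243 / 30.4375 = 7.98 months.

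**Step 2: room for enrolment.** Window = span minus participation, in months. Rows below 10 months are assumptions, because the number and spacing of treatments are redacted.

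| Participation | Longest span | Mid-month | Shortest span |
|---|---|---|---|
| 10 months | -0.05 | -1.03 | -2.02 |
| 9.5 months | 0.45 | -0.53 | -1.52 |
| 9 months | 0.95 | -0.03 | -1.02 |
| 8 months | 1.95 | 0.97 | -0.02 |
| 7 months | 2.95 | 1.97 | 0.98 |
| 6 months | 3.95 | 2.97 | 1.98 |

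At exactly 10 months for everyone the window is never positive. It opens as the course shortens, and at 7 months or less it is positive on every reading of the calendar.

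**Step 3: what would be needed for an assessment to be lost.** For the 12-week visit to fall by 31 May 2018, final treatment must be given by 31 May minus 84 days, which is 8 March 2018. For a last visit on 1 May the limit is 6 February 2018. A subject on a full 10-month course who enrols 1, 2 or 3 months after 1 August would finish 1.05, 2.05 or 3.05 months after 31 May (for example, 1 + 10 - 9.95 = 1.05). That visit is lost only if a rule stops follow-up on the planned date.

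**Step 4: is there such a rule?**

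- The dates appear in the Protocol Summary under a heading that marks them as planned.
- Section 4.4 gives a non-exhaustive list of reasons for terminating the study. A calendar date is not among them.
- Section 5.2.1 asks that each subject stay, if possible, until the required follow-up is complete.
- Section 9.2 turns on completing treatment. A treated subject who misses a follow-up visit stays in the analysis set.

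No readable text truncates treatment or follow-up in May 2018.

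**The case for a change.** The strongest case for a change is that both figures are readable, so redaction does not explain the mismatch. Section 4.2 does not say that 10 months is an upper limit, and it gives no range. Even if it is a maximum, a subject on the longest course would have to enrol at the very start to finish by May 2018. Allowing for the word approximately helps little: 9 months leaves at most 0.95 month, and about zero on mid-month dates. If 10 months was meant as the length of the whole study, Section 4.2 misdescribes it as individual participation. Subjects also accept restrictions for the duration (Section 5.1.1: smoking, other procedures, diet and weight, contraception), so the stated length should be accurate. The correction would take about two lines.

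What stands is that the two lines fit together poorly and that a sentence saying what the 10 months refers to would read better. August to May, counting both end months, is ten calendar months, which makes the whole-study reading plausible.

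The consequences do not stand. Loss of GAIS data or of subjects from analysis requires a cut-off that the readable text does not contain. What subjects are told cannot be judged either, because the consent pages are not available. An early-August enrollee seen in late May would in any case have 9.95 months, which is about 10. A demand for participation by number of treatments, or for a stated enrolment period, asks for items that may be in the redacted Section 6 or Appendix 1.

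**Conclusion.** No change to the plan is needed. The arithmetic is correct: the planned calendar spans 7.98 to 9.95 months, and a full 10 months for every subject leaves an enrolment window of -0.05 to -2.02 months. The contradiction is strict only if every subject needs the full 10 months, and Section 4.2 does not say that.

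The mismatch lies between a forecast date and an approximate duration. If enrolment takes longer than forecast, the last visit falls later than May 2018, as Section 5.2.1 already implies. Section 9.3 plans no hypothesis testing and Section 9.1 gives no sample-size calculation, so no error rate, power figure, estimate or safety rule depends on the planned month. Rewording would tidy the text without altering a result.

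This rests on two assumptions: that the redacted sections contain no rule closing follow-up on a fixed date, and that the Planned Schedule is the forecast its heading says it is.

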## 4.3 Study Assessments

### 4.3.1 Exploratory Assessments

Investigators will complete an assessment of the device along with the Global Aesthetic Improvement of the subjects from baseline vs. 12 weeks post first and last treatment.

### 4.3.2 Safety Assessments

Following the first treatment, adverse events (AEs) will be assessed post-treatment and at each subsequent visit using the following scale:

- 1= mild: requires minimal or no treatment and does not interfere with the subject's daily activities.
- 2= moderate: may cause some interference with functioning.
- 3= severe: interrupts subject's usual daily activity and may require treatment.

#### Treatment-related Discomfort:

After each treatment, subjects will be asked to rate the average amount of discomfort experienced during treatment and immediately after treatment using the Pain Rating Scale (VAS Scale) Appendix 2.

## 4.4 Study Discontinuation

Cutera, Inc. (the sponsor) has the right to terminate this study at any time. Reasons for terminating the study may include, but are not limited to, the following: incidence or severity of adverse events in this or other studies indicates a potential health hazard to subjects; subject enrollment is unsatisfactory; number of protocol deviations is unacceptable; data recording is inaccurate or incomplete; or questionable study site compliance with ICH-E6, Good Clinical Practice.

## 4.5 Investigator Selection

The Investigator(s) will be invited to participate in the study based on his or her medical specialty, experience conducting clinical research studies and experience in the use of RF devices for aesthetic indications. Access to potential study subjects and the Investigator's sincere interest in this study along with expressed willingness to cooperate with the study process and requirements are also considered.

## 5 STUDY POPULATION

### 5.1 Study Subject Recruitment and Selection

Approximately 40 male or female subjects, ages 18 to 65, who desire treatment with truSculpt. Subjects will be recruited to participate from the local population. Subjects may also be recruited from the

Investigator's existing patient database or from patients who present themselves to the study site requesting treatment. Only subjects who meet all eligibility criteria and who provide written informed consent will be enrolled into the study.

Each subject will be evaluated by the Investigator to assess his/her suitability for entry into the study according to the following inclusion and exclusion criteria.

### **5.1.1 Inclusion Criteria**

To be included in the study, subjects must meet all of the following Inclusion Criteria:

1. Subject must be able to read, understand and sign the Informed Consent Form.
2. Female or Male, 18 to 65 years of age (inclusive).
3. Subject has visible fat bulges in the area to be treated.
4. Non-smoking for at least 6 months and willing to refrain from smoking for the duration of the study.
5. Subject must agree to not undergo any other procedure(s) in the treatment region during the study period.
6. Subject must adhere to the follow-up schedule and study instructions.
7. Subject must adhere to the same diet and/or exercise routine throughout the study, and agree to maintain the same weight throughout the study.
8. Willing to have digital photographs taken of the treatment area and agree to use of photographs for presentation, (educational and/or marketing), publications, and any additional marketing purposes.
9. For female subjects: not pregnant or lactating and is either post-menopausal, surgically sterilized, or using a medically acceptable form of birth control at least 3 months prior to enrollment and during the entire course of the study.

### **5.1.2 Exclusion Criteria**

Subjects will be excluded from the study if they meet any of the following Exclusion Criteria:

1.	Participation in a clinical trial of another device or drug within 3 months of study participation, or during the study period.
2.	Any type of prior cosmetic treatment to the target area within 6 months of study participation.
3.	Any prior invasive cosmetic surgery to the target area, such as liposuction.
4.	Has a pacemaker, internal defibrillator, implantable cardioverter-defibrillator, nerve stimulator implant, cochlear implant or any other electronically, magnetically or mechanically activated implant.
5.	Has metal implant(s) within the body, such as artificial heart valves.
6.	Significant uncontrolled concurrent illness that in the opinion of the Investigator would make the subject unsuitable for inclusion.
7.	History of any disease or condition that could impair wound healing.
8.	History of keloid formation, hypertrophic scarring or abnormal/delayed wound healing.
9.	Skin abnormality in the treatment area that in the opinion of the Investigator would

	make the subject unsuitable for inclusion.
10.	Currently undergoing systemic chemotherapy or radiation treatment for cancer, or history of treatment in the target area within 3 months of study participation.
11.	As per the Investigator's discretion, any physical or mental condition which might make it unsafe for the subject to participate in this study or a condition that would compromise the subject's ability to comply with the study requirements.

## 5.2 Subject Numbering

If a subject completes the Informed Consent Form, meets the study eligibility criteria and is willing to participate, the subject will be assigned a study subject identification number. This number is comprised of a site number (which is provided by the sponsor) and a sequential subject number and the subject initials (first and last names).

### 5.2.1 Subject Discontinuation Criteria

If possible, every subject should remain in the study until completion of the required follow-up period. However, participation in this study is completely voluntary and a subject can choose to withdraw from the study at any time. Decision to withdraw will not affect or prejudice the subject's continued medical care in any way. In those instances, the investigator will attempt to obtain a final clinical assessment and an adverse device effect evaluation for the subject prior to this withdrawal. A subject will be considered lost to follow-up only after three unsuccessful, documented attempts to contact the subject have been made.

In addition, a subject can be discontinued for any of the following reasons: the Principal Investigator decides that continuing in the study would not be in the subject's best interest, a subject is noncompliant with the protocol, a subject has a serious reaction to the treatment, a subject develops any of the exclusion criteria during the study period or the study is stopped by the study sponsor.

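### Section 5.2.1 does not separate stopping treatment from leaving follow-up, so a subject discontinued for a treated-area reaction can lose later safety follow-up and the 12-week GAIS

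*Protocol*

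**What the plan says.** Section 5.2.1 opens with a retention aim: if possible, "every subject should remain in the study until completion of the required follow-up period". It then deals with voluntary withdrawal, and for that case says that "the investigator will attempt to obtain a final clinical assessment and an adverse device effect evaluation for the subject prior to this withdrawal". A separate paragraph lists further reasons for which a subject may be discontinued. Two of them matter here: "a subject has a serious reaction to the treatment" and "a subject develops any of the exclusion criteria during the study period". The others are the investigator's view of the subject's best interest, non-compliance, and a stop by the sponsor. No final assessment is mentioned for this second group, and nothing says whether discontinuation means the end of treatment or the end of participation.

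The exclusion criteria that the rule brings in are in section 5.1.2. Criterion 9 begins "Skin abnormality in the treatment area that in the opinion of the Investigator would" and goes on to unsuitability for inclusion. Criterion 8 reads "History of keloid formation, hypertrophic scarring or abnormal/delayed wound healing". Criteria 2 and 3 read "Any type of prior cosmetic treatment to the target area within 6 months of study participation" and "Any prior invasive cosmetic surgery to the target area, such as liposuction".

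Four other places bear on the point:
- Sections 4.1.1 and 4.1.2 make adverse device events the safety endpoint, and GAIS 12 weeks after the first and the final treatment an exploratory endpoint.
- Section 7.3 follows events to resolution or to the end of participation.
- Section 9.2 restricts the analysis sets to enrolled subjects who complete treatment.
- Section 9.4 counts each adverse event term once per subject, at its worst severity and longest duration.

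**The concern.** The exclusion list was written to screen subjects before treatment. Section 5.2.1 applies the whole list to what happens afterwards. At that stage, a skin abnormality in the treated area may be something the device caused. A safety outcome can then be the reason that observation of the subject ends. The serious-reaction reason in the same sentence works the same way and more directly. The exclusion-criteria reason adds non-serious local effects, because criterion 9 rests on the investigator's opinion.

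If leaving the study depends on the outcome, the subjects who remain look better than the subjects who were treated. No control arm is described and no hypothesis test is planned, so the descriptive rates are the result of the study. With about 40 subjects, a few such exits are visible in those rates.

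**Working it through.** The plan states no figure for this point. The sample size of 40 in section 9.1 is a judgement with no dropout allowance, so there is nothing to reproduce. The check is first one of wording.

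**Step 1: can a trigger be an outcome?** Section 5.2.1 speaks of criteria that a subject develops during the study, so the protocol itself applies the list after enrolment. Criterion 9 fits that use: it names a current condition in the treatment area. Criterion 8 fits less well, because it is worded as history. If either condition arises after treatment and is device-related, it is an adverse device event under section 4.1.1. Criteria 2 and 3 are worded as prior treatment. Another procedure during the study is a breach of inclusion criterion 5 and an intercurrent event, not an endpoint.

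**Step 2: what happens to that subject's data?**
- *The event itself:* recorded. Section 7.2 requires all events from the first treatment to be entered with severity, dates and outcome. Section 7.3 also requires device events leading to permanent discontinuation to go on the non-completion form.
- *Its later course:* not secured. Section 7.3 lets follow-up end with participation. The worst severity and longest duration that section 9.4 reports are then cut off at the exit date.
- *Final assessment:* the attempt is tied to voluntary withdrawal and not repeated for exits decided by the investigator.
- *12-week GAIS:* missing if exit comes before the visit.
- *Place in the tables:* lost if treatment was not completed and section 9.2 governs safety. The GAIS timing distinguishes a first from a final treatment, so an exit between treatments is possible.

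**Step 3: illustrative size, safety.** Input from the documents: N = 40. Assumed: k subjects have a device event, all exit before completing treatment, section 9.2 governs the safety tables, and nobody else has such an event. The true rate is k/40 and the rate shown is 0/(40 − k). Upper limits are exact (Clopper-Pearson) two-sided 95% limits; for zero events in n subjects the limit is 1 − 0.025^(1/n).

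| k | All treated | Upper limit | Shown | Upper limit |
|---|---|---|---|---|
| 1 | 1/40 = 2.5% | 13.2% | 0/39 | 9.0% |
| 2 | 2/40 = 5.0% | 16.9% | 0/38 | 9.3% |
| 4 | 4/40 = 10.0% | 23.7% | 0/36 | 9.7% |

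**Step 4: illustrative size, GAIS.** Assumed: r of 40 subjects improve, and all k exits are among those who do not. The share shown is r/(40 − k).

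| Assumed true share | k = 2 | k = 4 |
|---|---|---|
| 20/40 = 50% | 20/38 = 52.6% | 20/36 = 55.6% |
| 28/40 = 70% | 28/38 = 73.7% | 28/36 = 77.8% |
| 32/40 = 80% | 32/38 = 84.2% | 32/36 = 88.9% |

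The gain is about 3 to 4 points for two exits and 6 to 9 points for four. The visible text does not define improvement on the GAIS, so a yes/no share is itself an assumption.

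**The case against.** The best defence is that the rule is permissive, that section 5.2.1 starts from keeping every subject to the end of follow-up where possible, and that sections 7.2 and 7.3 capture the event that leads to an exit. The study procedures in section 6 and the opening of section 7 are redacted, so an early-exit visit may be described there. All of this stands, and it limits the loss to the later course of the event and the 12-week rating. It does not remove the problem: the retention aim is general, and the permission that follows it is specific. Section 7.3, which is visible, still lets follow-up stop when participation does.

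A reader might go further and infer that several exclusion criteria are themselves trial outcomes, including another cosmetic procedure. The documents do not support that. Criteria 2, 3 and 8 are worded as prior treatment or history. Another procedure is already covered by non-compliance in the same list, so the exclusion-criteria clause is not needed for that exit. It may reflect dissatisfaction, and leaving because of it also removes the GAIS selectively, but this is the weaker route.

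A reader might also infer that harms vanish from the record. They need not. An event drops out of the safety table only if the subject had not completed treatment and section 9.2 is applied to safety.

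**Conclusion.** The point holds in a limited form. As written, section 5.2.1 allows outcome-dependent exit from the whole study, and sections 7.3 and 9.2 do nothing to offset it. What is at risk is the later course, maximum severity and duration of a treated-area event, the 12-week GAIS and, for subjects who stop before completing treatment, their place in the tables. Each of these losses would tend to favour the device.

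The size cannot be determined from the documents, because they give no event or exit rates. Two exits in 40 would turn 5% into 0/38 and lower the exact upper limit from 16.9% to 9.3%. The safety figures assume that every affected subject exits before completing treatment. The GAIS figures assume that every exit is a subject who did not improve. Both are upper-end cases for a given number of exits.

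A reader might conclude that the trigger itself should be confined to conditions present before the first treatment. That does not follow. It would contradict the word 'develops', remove the named reason for new implants or chemotherapy, and leave the serious-reaction route untouched. The fault lies in what discontinuation ends, not in the list of reasons.

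**What to change.** Leave the discontinuation reasons and all treatment decisions as they are. Add to section 5.2.1:

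1. Discontinuation for any investigator-initiated reason ends study treatment only. Unless the subject withdraws consent or the study is stopped, the subject stays in for the scheduled adverse event follow-up and the 12-week GAIS. This includes subjects who have another procedure in the treated region.
2. The final clinical assessment and the adverse device effect evaluation are attempted for every early exit, not only for voluntary withdrawal.

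Then reconcile two other sections. Section 7.3 should make clear that stopping treatment is not the end of participation for event follow-up. Section 9.2 should keep treated subjects who did not complete treatment in the safety tables. How GAIS ratings after another procedure are analysed can be left to the SAP.

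The cost is two or three sentences in section 5.2.1 and matching edits in sections 7.3 and 9.2. The visits are already scheduled. The downside is a few more completed visits and possibly less favourable rates.
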